9.5. Physical Examination

The number and percentage of subjects with normal and abnormal findings in the complete physical examination, including nasal passages examination, will be displayed for each treatment group, subjects not randomized and overall subjects by study visit for the Safety Population. Abnormal results will be grouped as clinically significant and not clinically significant.

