13.1.5.5 Physical Examination Findings

The number and percentage of subjects with normal and abnormal findings in the complete physical examination, including nasal passages examination, will be displayed for each treatment group.

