2.2.2. Safety Endpoints

The safety endpoints are mapped to the safety objective as follows:

Safety Objective

The safety objective of the study is to determine safety and tolerability of PH94B compared to placebo in adult subjects with SAD from reported AEs and changes in vital signs, 12-lead ECGs, laboratory parameters, suicidality, level of depression, and physical examinations.

Safety Endpoints

Incidence and severity of AEs

Changes in vital signs results

Changes in clinical laboratory evaluation (hematology, chemistry, and urinalysis) results

Changes in 12-lead ECG results

Changes in physical examination findings

[figure not shown]
Mean HAM-D scores

[figure not shown]
Incidence of treatment-emergent suicidal ideation and behavior

3. Overall Study Design and Plan

3.1. **Overall Design**

The study is a Phase 3, multicenter, randomized, double-blind, placebo-controlled, parallel design, single-dose, clinical trial of the efficacy, safety, and tolerability of the acute administration of PH94B to relieve symptoms of acute anxiety in adult subjects with SAD.

Efficacy assessments for the primary endpoint will be completed at Visit 2 (Baseline) and Visit 3 (Treatment). Efficacy assessments for the secondary endpoint will be completed at Visit 3 (Treatment). Safety assessments are completed at Visit 1 (Screening) and Visit 4 (Follow-Up), with the exception of vital signs assessments, pregnancy tests, and Columbia-Suicide Severity Rating Scale (C-SSRS), which are completed at all visits, and AE recordings, which are completed starting at Visit 2 (Baseline). Refer to the Schedule of Events (Table 1) for more detail.

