9.2. Clinical Laboratory Evaluations

Descriptive summaries of observed values and change from baseline values will be presented for continuous hematology, chemistry, and urinalysis results for each treatment group, subjects not randomized and overall subjects at each study visit. Categorical urinalysis results will be summarized using frequencies by treatment group, subjects not randomized and overall subjects and by study visit.

The number of subjects with clinical laboratory values categorized as below, within, or above normal ranges will be tabulated showing change from baseline (shift tables) for each clinical laboratory analyte by treatment group and overall subjects and by study visit.

Laboratory values that are outside the normal range will also be flagged in the data listings and presented with the corresponding normal ranges. Any out-of-range values that are identified by the investigator as being clinically significant will be listed as an adverse event.

For women only, pregnancy status will be determined by evaluation of urine pregnancy test. Data on pregnancy status will be listed by subjects. Subjects who are pregnant are excluded from the study. Subjects who become pregnant during the study will be discontinued.

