9.3. Vital Signs

Descriptive summaries of observed values and changes from baseline will be calculated for systolic blood pressure (mmHg), diastolic blood pressure (mmHg), heart rate (beats/min), respiratory rate (breaths/min), and temperature (°C) by treatment group, subjects not randomized and overall subjects and by study visit.

The number of subjects with vital signs values categorized as below, within, or above normal ranges will be tabulated showing change from baseline (shift tables) for each parameter by visit by treatment group and overall.

9.4. 12-Lead Electrocardiograms

The number and percentage of subjects with normal and abnormal 12-lead ECG findings will be summarized for each treatment group, subjects not randomized and overall subjects at each study visit. Abnormal results will be grouped as clinically significant and not clinically significant.

Descriptive summaries for the observed results and change from baseline will be presented for 12-lead ECG measures of PR interval (msec), QRS interval (msec), and heart rate for each treatment group and overall subjects at each study visit. If triplicate reads are taken, the mean of the reads will serve as the observed value at the specific visit.

A comparison of QT and QTcF results will be presented. Summary statistics for baseline values at Visit 1 (Screening) and Visit 4 (Follow-Up) will be displayed by treatment group and overall subjects for QT interval (msec) and QT interval corrected for heart rate using Fridericia's formula (QTcF) (msec). In addition, the number and percent of subjects in each treatment group who experienced a change >30 msec or a change >60 msec will be presented.

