Table 14.3.5.3.3	Safety	Quantitative and Qualitative Urinalysis: Shifts from Baseline Relative to the Normal Range	
14.3.6 Other Safe	ety Data Summary	Tables	
Table 14.3.6.1.1	Safety	Vital Signs: Observed Results and Change from Baseline by Study Visit	

Table Number	Population	Table Title / Summary	
Table 14.3.6.1.2	Safety	Vital Signs: Shifts from Baseline Relative to Normal Range by Stud Visit	
Table 14.3.6.2.1	Safety	12-Lead Electrocardiogram: Observed Results and Change from Baseline by Study Visit	
Table 14.3.6.2.2	Safety	12-Lead Electrocardiogram: Summary of 12-Lead Electrocardiogram Interpretation by Study Visit	
Table 14.3.6.2.3	Safety	12-Lead Electrocardiogram: Summary of QT and QTcF Results by Study Visit	
Table 14.3.6.3	Safety	Summary of Physical Examination by Study Visit	
Table 14.3.6.4	Safety	Summary of Concomitant Medications by ATC Class and Preferred Term	
Table 14.3.6.5	Safety	Summary of Columbia Suicide Severity Rating Scale (C-SSRS) by Study Visit	
Table 14.3.6.6	Safety	Hamilton Depression Scale (HAM-D): Observed Results and Change from Baseline by Study Visit	

Table 6: Other Data Summary Tables

Table Number Population		Table Title / Summary	
14.5 Other Data	Summary Tables		
Table 14.5.1	able 14.5.1 Safety Summary of Drug Prediction Questionnaire (DPQ)		

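### Change in physical examination findings is a safety endpoint, but the planned table gives only by-visit counts and does not report how many subjects became abnormal after Screening.

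*SAP*

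**What the plan says.** SAP 2.2.2 lists "Changes in physical examination findings" among seven safety endpoints, and protocol 6.4 maps the same endpoint to the safety objective. The protocol synopsis, under safety considerations, says safety will be summarised through changes from screening and includes physical examinations. SAP Table 2 (section 6.1.1) defines a baseline for physical examinations: the last non-missing assessment before the first dose at Visit 2. SAP Table 1 schedules the examination, including the nasal passages, at Visits 1 and 4.

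The planned analysis is in SAP 9.5: "The number and percentage of subjects with normal and abnormal findings in the complete physical examination, including nasal passages examination, will be displayed" by treatment group, subjects not randomised, overall, and study visit. It adds: "Abnormal results will be grouped as clinically significant and not clinically significant". Protocol 13.1.5.5 plans the same counts by treatment group. The output in SAP 13.3 is Table 14.3.6.3, titled "Summary of Physical Examination by Study Visit".

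Other safety variables are handled differently. Laboratory values are "tabulated showing change from baseline (shift tables) for each clinical laboratory analyte" (SAP 9.2). Vital signs are "tabulated showing change from baseline (shift tables) for each parameter by visit by treatment group and overall" (SAP 9.3).

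**The concern.** The endpoint is a within-subject change, and the planned table is a pair of cross-sectional summaries. The SAP defines a baseline for the examination, but section 9.5 does not use it. A reader of Table 14.3.6.3 would see how many subjects were abnormal at each visit. They would not see how many who were normal at Screening had become abnormal by Visit 4.

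This matters somewhat more here than in most trials. The product is given intranasally, protocol 5.3 names local reactions in the nose as a possible risk, and protocol 7.2 says the nasal examination was included because of the route. Exclusion criteria 4 and 5 remove clinically significant nasal pathology, uncontrolled allergies and significant congestion, so minor nasal findings at Screening remain possible. Where some subjects start abnormal, new findings and resolved findings offset each other in by-visit counts.

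**Working it through.** The documents give no figure to reproduce. The check sets the endpoint against the outputs and then asks what by-visit counts can identify.

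**1. Endpoint against output.**

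| Endpoint (SAP 2.2.2) | Within-subject summary planned |
|---|---|
| Laboratory | Change from baseline and shift tables (SAP 9.2) |
| Vital signs | Change from baseline and shift tables (SAP 9.3) |
| ECG | Change from baseline for PR, QRS and heart rate; counts with QT/QTcF change >30 and >60 msec (SAP 9.4). None for the normal/abnormal interpretation (Table 14.3.6.2.2) |
| HAM-D | Change from baseline (SAP 9.8) |
| Suicidality | Treatment-emergent counts (SAP 9.7) |
| Physical examination | None (SAP 9.5, Table 14.3.6.3) |

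**2. What by-visit counts identify.** Let n subjects be examined at both visits, with *a* abnormal at Visit 1 and *b* at Visit 4. Let *x* be the number going from normal to abnormal and *r* the number going from abnormal to normal. Then

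b = a + x − r.

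The table therefore fixes the net change, x − r = b − a. It does not fix *x*, which satisfies only

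max(0, b − a) ≤ x ≤ min(b, n − a).

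Take n = 104, the planned arm size (SAP 3.2). The abnormal counts are assumptions, because the documents give none.

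| a (Visit 1) | b (Visit 4) | Possible x |
|---|---|---|
| 5 | 5 | 0 to 5 |
| 10 | 10 | 0 to 10 |
| 20 | 20 | 0 to 20 |
| 10 | 15 | 5 to 15 |
| 15 | 10 | 0 to 10 |

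**3. The extreme bound.** Suppose both arms show 10 of 104 (9.6%) abnormal at both visits, so that 104 − 10 = 94 per arm were normal at Screening. The planned tables would be identical, yet new abnormalities could be 10/94 in one arm and 0/94 in the other (Fisher exact p = 0.0015). With 5 abnormal at both visits the extreme is 5/99 against 0/99 (p = 0.059). With 15 it is 15/89 against 0/89 (p = 0.00003). These p-values only mark how much the table leaves open; the SAP plans no formal safety testing.

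**4. What the other outputs recover.**
- Listing 16.2.9.3 gives physical examination data by subject, and SAP 6.1.8 says all collected data are listed. Visits 1 and 4 can be compared subject by subject, but a listing is not a summary of the endpoint.
- A condition present at screening counts as baseline and its deterioration is an adverse event (protocol 11.2; SAP 9.1). Clinically relevant observations at a visit are also adverse events (protocol 11.2.1). Treatment-emergent events are tabulated separately for the period before Visit 3 dosing and the period during or after it (SAP 9.1).
- What remains untabulated is mainly new findings that the investigator does not judge clinically relevant. SAP 9.5 itself considers findings that are not clinically significant worth counting.

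**The case against.** The strongest reply is that little is lost. Randomisation allows Visit 4 abnormal rates to be compared between arms, apart from chance and dropout. An excess of new findings on PH94B would raise its Visit 4 rate unless PH94B also resolved a similar excess of old ones. The 10/94 against 0/94 case needs all 10 abnormal subjects in one arm to normalise while 10 others become abnormal, with nobody changing in the other arm. This reply stands: the case is a bound, not an expectation. It does not make the table report change.

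Stronger readings that a reader might infer, and why the documents do not support them:

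- **That new nasal or physical abnormalities cannot be separated from old ones.** The listing and the adverse event rules both separate them. The limit applies to the summary table.
- **That SAP 9.5 counts only normal and abnormal.** It also splits abnormal results by clinical significance.
- **That the nasal examination is the only objective local measure.** Listing 16.2.9.4 is for a Quick Olfactory Test, whose purpose and timing are not visible. The reactions named in protocol 5.3 are largely symptoms, which adverse event recording captures, and that section says none was reported in more PH94B than placebo subjects.
- **That the overall column misleads because dosed subjects who were not randomised contribute at Screening but mostly not at Visit 4.** SAP 9.5 gives those subjects their own column, so the composition is visible, and the overall column plays no part in comparing PH94B with placebo.
- **That nasal findings will be buried in the complete examination.** Only the title of Table 14.3.6.3 is visible, so a separate nasal row may already exist.

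A shift table also has its own limit. With examinations only at Visits 1 and 4, it includes changes during up to 35 days of screening and after the Visit 2 placebo dose.

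**Conclusion.** The point holds as a modest mismatch between endpoint and table. The endpoint is a change, and the planned summary does not report how many subjects went from normal at Screening to abnormal at Visit 4. The size of the gap depends on how many subjects are abnormal at Screening, which the documents do not state. If very few are, by-visit counts and a shift table say nearly the same thing. In the illustration, 5 to 20 abnormal per arm at both visits leaves the number newly abnormal undetermined over ranges of 0–5 to 0–20.

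The documents do not show that a safety signal would be missed. Clinically relevant or worsened findings have a tabulated route as adverse events, and Visit 4 rates remain comparable between arms. This is an inexpensive improvement to one of seven descriptive safety endpoints, and it brings the examination into line with the laboratory and vital sign tables.

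**What to change.** In SAP 9.5, add to Table 14.3.6.3 a shift from Visit 1 to Visit 4 in three categories: normal, abnormal not clinically significant, and abnormal clinically significant. Present it for the PH94B and placebo groups, restricted to subjects with both examinations. Show nasal passages separately from the rest of the examination. Report the number newly abnormal over the number normal at Screening. Keep the by-visit counts.

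Add the same shift for ECG interpretation (Table 14.3.6.2.2). State in SAP 9.5 that the shift covers the whole interval from Screening, so attribution to PH94B rests on comparing the arms.

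The data are already collected and no procedure changes. The cost is slightly more safety-table programming and review.

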9.6. Concomitant Medication

Prior and concomitant medications will be summarized descriptively by treatment using counts and percentages for the Safety Population. Medications will be summarized by treatment group, by the number and percentage of subjects taking each medication and classified by ATC class and preferred term. Data will also be presented in a by-subject listing, which will include ATC Level 2 classification, preferred term and verbatim name.

Prior medications will be presented separately from concomitant medications. All medications taken in the month prior to Visit 1 (Screening) or in the time interval between Visit 1 (Screening) and Visit 2 (Baseline) will be considered prior medications, whether or not they were stopped

before Visit 2 (Baseline). Any medications continuing or starting after Visit 2 (Baseline) will be considered concomitant. If a medication starts before Visit 2 (Baseline) and continues after Visit 2 (Baseline) it will be considered concomitant.

Medications will be coded using WHO-DD, as described in Section 6.1.8.

9.7. Columbia-Suicide Severity Rating Scale (C-SSRS)

The number and percentage of subjects reporting "Yes" for any of the 5 suicidal ideation questions (Categories 1 to 5) or any of the 5 suicidal behavior questions (Categories 6 to 10) will be displayed for each treatment group and overall subjects, along with the number and percentage reporting suicidal ideation OR behavior (Categories 1 to 10). The number and percentage of subjects with treatment emergent suicidal ideation, treatment emergent suicidal behavior, and treatment emergent suicidal ideation or behavior as defined in Section 6.1.7.8 will also be presented.

9.8. Hamilton Depression Scale (HAM-D)

Total scores and change from baseline will be summarized by visit and by treatment group and overall subjects for the Safety Population.

10. Other Planned Analyses

10.2. Coronavirus 2019 (COVID-19) Impact

The SARS-CoV-2 virus and variants may still be a threat and safety precautions may still be in place during study enrollment. To assess the impact of the COVID-19 pandemic on study procedures, study staff will complete the COVID-19 Impact questionnaire. Should a study visit be affected by COVID-19, study staff will record how the visit was affected (missed, abbreviated, delayed, performed remotely, or otherwise deviating from the planned format in the protocol) and which procedures were impacted. All COVID-19 protocol deviations will be provided in a separate listing. This listing will include the subjects, affected visits, and affected assessments.

11. Changes from Planned Analysis

Study staff will complete the Coronavirus 2019 (COVID-19) Impact questionnaire to assess the impact of the COVID-19 pandemic on study procedures. The COVID-19 Impact questionnaire is described in Section 10.2. All COVID-19 protocol deviations will be provided in a separate listing.

The All Subjects Population was explicitly defined for programming purposes and will be used for summaries of subject disposition and protocol deviations.

The PP Population was defined and will be used for a sensitivity analysis of the primary endpoint.

Race was added as a subgroup of interest for the subgroup analyses.

12. References

ASA. (2018) Ethical Guidelines for Statistical Practice. Prepared by the Committee on Professional Ethics, April 2018. http://www.amstat.org/about/ethicalguidelines.cfm

Carpenter JR and Kenward MG. Multiple Imputation and its Application (Statistics in Practice). Chichester, West Sussex, UK: John Wiley & Sons; 2013.

Graham JW, and Olchowski AE, Gilreath TD. (2007) "How Many Imputations are Really Needed? Some Practical Clarifications of Multiple Imputation Theory." *Prev Sci.* 2007;8(3): 206-213.

ICH (1998). ICH Harmonised Tripartite Guideline. Statistical Principles for Clinical Trials E9; 1998. https://database.ich.org/sites/default/files/E9 Guideline.pdf

Little R and Rubin D. (1987). Statistical Analysis with Missing Data, New York: Wiley.

RSS. (2014) The Royal Statistical Society: Code of Conduct, 2014. https://rss.org.uk/about/policy-and-guidelines/code-of-conduct/.

13. Tables, Listings, and Figures

All listings, tables, and graphs will have a header showing the sponsor company name and protocol and a footer showing the version of SAS, the file name and path, and the source of the data (e.g., listing number).

The following are planned summary tables for protocol number PH94B-CL032. The table numbers and page numbers are place holders only and will be determined when the tables are produced.

[figure not shown]
Table 3: Demographic Data Summary Tables and Figures

Table Number	Population	Table Title/Summary		
14.1 Demographic Data Summary Tables and Figures				
Table 14.1.1.1.1	All Subjects	Subject Enrollment and Disposition		
Table 14.1.1.1.2	ITT	Subject Enrollment and Disposition		
Table 14.1.1.2	All Subjects	Protocol Deviations		
Table 14.1.2.1	Safety	Demographics and Baseline Characteristics		
Table 14.1.2.2	ITT	Demographics and Baseline Characteristics		
Table 14.1.2.3	PP	Demographics and Baseline Characteristics		
Table 14.1.3	Safety	Medical and Psychiatric History by System Organ Class and Preferred Term		
Table 14.1.4	Safety	Prior Medications by ATC Class and Preferred Term		
Table 14.1.5	Safety	Baseline Summary of Mini International Neuropsychiatric Interview (MINI)		
Table 14.1.6	Safety	Baseline Summary of Social Anxiety Disorder (SAD) Diagnostic Checklist		
Table 14.1.7	Safety	Exposure to Investigational Product		

13.2. Efficacy Data

Table 4: Efficacy Data

Table Number	Population	Table Title / Summary	
Table 14.2. Effica	acy Tables		
Table 14.2.1.1	ITT	ANCOVA Change from Baseline in Average SUDS Scores – Primary Analysis	
Table 14.2.1.2	ITT	ANCOVA Change from Baseline in Average SUDS Scores – Sensitivity Analysis Using Complete Cases	
Table 14.2.1.3	PP	ANCOVA Change from Baseline in Average SUDS Scores by Analysis Visit – Per Protocol Sensitivity Analysis	
Table 14.2.2	ITT	Analysis of the Proportion CGI-I Responders – Secondary Analysis	
Table 14.2.3.1	ITT		
Table 14.2.3.2	ITT		

13.3. Safety Data

Table 5: Safety Data

Table Number	Population	Table Title / Summary	
14.3.1 Displays of	Adverse Events		
Table 14.3.1.1	Safety	Overall Summary of Treatment Emergent Adverse Events	
Table 14.3.1.2.1	Safety	Treatment Emergent Adverse Events by System Organ Class and Preferred Term	
Table 14.3.1.2.2	Safety	Treatment Emergent Adverse Events by Preferred Term	
Table 14.3.1.3	Safety	Treatment Emergent Adverse Events by System Organ Class, Preferred Term, and Maximum Severity	

Fable Number Population		Table Title / Summary	
Table 14.3.1.4	Safety	Treatment Emergent Adverse Events by System Organ Class, Preferred Term, and Maximum Relationship to Investigational Product	
14.3.2 Summary	of Deaths, Other Se	erious and Significant Adverse Events	
Table 14.3.2.1	Safety	Treatment Emergent Adverse Events Leading to Study Discontinuation by System Organ Class and Preferred Term	
Table 14.3.2.2	Safety	Serious Treatment Emergent Adverse Events by System Organ Class and Preferred Term	
Table 14.3.2.3	Safety	Serious Treatment Emergent Adverse Events Related to Investigational Product by System Organ Class and Preferred Term	
14.3.3 Narratives	of Deaths, Other S	Serious and Certain Other Significant Adverse Events	
Table 14.3.3.1	Safety	Subject Listing of Serious Adverse Events	
Table 14.3.3.2	Safety	Subject Listing of Adverse Events Leading to Discontinuation of Investigational Product	
Table 14.3.3.3	Safety	Subject Listing of Adverse Events Leading to Death	
14.3.4 Abnormal	Laboratory Values	S :	
Table 14.3.4.1	Safety	Subject Listing of Abnormal Laboratory Values: Clinical Chemistry and Thyroid	
Table 14.3.4.2	Safety	Subject Listing of Abnormal Laboratory Values: Hematology	
Table 14.3.4.3	Safety	Subject Listing of Abnormal Laboratory Values: Urinalysis	
14.3.5 Laborator	y Data Summary T	ables	
Table 14.3.5.1.1	Safety	Clinical Chemistry and Thyroid: Observed Results and Change and Percent Change from Baseline by Study Visit	
Table 14.3.5.1.2	Safety	Clinical Chemistry and Thyroid: Shifts from Baseline Relative to the Normal Range	
Table 14.3.5.2.1	Safety	Hematology: Observed Results and Change and Percent Change from Baseline by Study Visit	
Table 14.3.5.2.2	Safety	Hematology: Shifts from Baseline Relative to the Normal Range by Study Visit	
Table 14.3.5.3.1	Safety	Quantitative Urinalysis: Observed Results and Change and Percent Change from Baseline by Study Visit	
Table 14.3.5.3.2	Safety	Qualitative Urinalysis: Summary of Results by Study Visit	
Table 14.3.5.3.3	Safety	Quantitative and Qualitative Urinalysis: Shifts from Baseline Relative to the Normal Range	
14.3.6 Other Safe	ety Data Summary	Tables	
Table 14.3.6.1.1	Safety	Vital Signs: Observed Results and Change from Baseline by Study Visit	

Table Number	Population	Table Title / Summary	
Table 14.3.6.1.2	Safety	Vital Signs: Shifts from Baseline Relative to Normal Range by Stud Visit	
Table 14.3.6.2.1	Safety	12-Lead Electrocardiogram: Observed Results and Change from Baseline by Study Visit	
Table 14.3.6.2.2	Safety	12-Lead Electrocardiogram: Summary of 12-Lead Electrocardiogram Interpretation by Study Visit	
Table 14.3.6.2.3	Safety	12-Lead Electrocardiogram: Summary of QT and QTcF Results by Study Visit	
Table 14.3.6.3	Safety	Summary of Physical Examination by Study Visit	
Table 14.3.6.4	Safety	Summary of Concomitant Medications by ATC Class and Preferred Term	
Table 14.3.6.5	Safety	Summary of Columbia Suicide Severity Rating Scale (C-SSRS) by Study Visit	
Table 14.3.6.6	Safety	Hamilton Depression Scale (HAM-D): Observed Results and Change from Baseline by Study Visit	

Table 6: Other Data Summary Tables

Table Number Population		Table Title / Summary	
14.5 Other Data	Summary Tables		
Table 14.5.1	able 14.5.1 Safety Summary of Drug Prediction Questionnaire (DPQ)		

